2.1 Trial Design

This is an assessor blinded cluster randomized controlled trial with rhythmic gymnastics clubs as the unit of randomization. Two different interventions (preventive exercises for the knees, lower back and hip/groin and pelvic floor muscle training (PFMT)) for two different conditions (overuse injuries and UI) are combined in this design. After inclusion, all rhythmic gymnastics clubs will be randomly allocated 1:1 to preventive exercises for knee, lower back and hip/groin and PFMT or a control group with no intervention.

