2.3 Sample size

The power calculation for Publication I (overuse injuries) is based on average prevalence in our previous study (Gram, M., Clarsen, B., & Bø, K., 2021) and previous studies with a

STATISTICAL ANALYSIS PLAN for NCT05506579

similar design (Olsen, et.al, 2005). With 80% power, 5% significance level and a decrease in the primary outcome measure from 40% to 20% in the intervention group and no change in the control group at least 158 gymnasts are required. In addition, to account for randomization at the cluster level, the total number were multiplied with an inflation factor (DE) of 1.4 (based on the following assumptions; average number of gymnasts per club (cluster) $m = 9$, $ICC = 0.05$, $DE = 1+(m - 1)*ICC = 1+(9 - 1)*0.05 = 1.4$), resulting in a required total sample size of 220 gymnasts (110 in each group).

The power calculation for Publication II (UI) is based on average prevalence in our previous study (Gram, M., & Bø, K., 2020) and studies with a similar design (Ferreira, et.al, 2014). With 80% power, 5% significance level and a decrease in the total sum score of ICIQ from 4.7 to 2.5 (SD 2.1) in the intervention group and no change in the control group at least 30 gymnasts are required. Multiplied with the same DE, the total required sample size will be 42 gymnasts (with 21 in each group).

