2.4.2 Decision Rule

This RCT is designed to address a single primary outcome for each publication. Superiority of the intervention is claimed if the primary null hypothesis is rejected on the significance level (alpha) of 0.05 (two-sided).

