5.2 Analysis Methods

5.2.1 Publication 1

The outcomes prevalence of overuse injuries (primary outcome) and prevalence of substantial overuse injuries (secondary outcome) will be analyzed with multilevel mixed effect logistic regression models. The models will be fitted with outcome data from all time points (Nov, Dec, ..., June) except the baseline (Oct). The models will have a fixed effect for group (intervention vs control) and two random intercepts: gymnast and club, with gymnast nested within club. Based on the fitted model, we will present the odds ratio (OR) for injury (with 95% confidence interval [CI]) for intervention vs control and the P-value for the null hypothesis of an OR = 1.

The observed prevalence of injuries (with 95% CI) for each time point (Oct, Nov, ..., June) for the primary outcome and the secondary outcome I) and II) will be presented in a figure.

Self-experienced effect and progress is measures on a -5 to 5 scale and only measured after end of the intervention (June) and only for the gymnasts in the intervention group. We will present the observed number and percentage of responses in each category (-5, -4, ..., 4, 5) and also the mean and standard deviation of the responses.

5.2.2 Publication 2

Bother of UI (primary outcome) at the end of the intervention (June) will be analyzed with linear regression, with the June measurement as the dependent variable and group (intervention vs control) and the baseline (Oct) measurement as independent variables (ANCOVA). The standard errors in the model will be adjusted for the clustering of gymnasts within clubs. We will present the mean and standard deviation of the baseline and end-of-intervention measurements for each group and the estimated between-group difference in changes from baseline to end-of-intervention with a 95% CI. We will also give the P-value for the null hypothesis of a zero between-group difference.

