The prevalence of UI (secondary outcome) at the end of the intervention (June) will be analyzed with a mixed effect logistic regression model with the June measurement as dependent variable and group (intervention vs control) and the baseline (Oct) measurement as independent variables. The model will contain a random intercept for club to account for the clustering of gymnasts within clubs. We will present the observed prevalence of UI for each group for each of the two time points, the OR for UI (with 95% CI) for intervention vs control and the P-value for the null hypothesis of an OR = 1.

Self-experienced effect and progress will be analyzed as described in section 5.2.1.

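### SAP section 5.2.1 names no small-sample reference for the Publication I primary mixed logistic model, although the planning figures imply only about 24 clubs

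*SAP*

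**What the plan says.** Section 2.1 describes a "cluster randomized controlled trial with rhythmic gymnastics clubs as the unit of randomization". Section 5.2.1 fits the eight monthly outcomes from November to June with a multilevel logistic model: "The models will have a fixed effect for group (intervention vs control) and two random intercepts: gymnast and club, with gymnast nested within club". From that fit it promises an odds ratio, a 95% confidence interval and a P-value. Section 6 names Stata 17. No section gives degrees of freedom for clubs, a small-sample correction, a permutation test or a club-level analysis, or says whether the P-value is a Wald or a likelihood-ratio one.

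Section 2.4.2 attaches the claim to this P-value: "Superiority of the intervention is claimed if the primary null hypothesis is rejected on the significance level (alpha) of 0.05 (two-sided". Section 2.4.1 makes it the only primary analysis of Publication I.

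The number of clubs is not stated. Section 2.3 gives "average number of gymnasts per club (cluster) $m = 9$, $ICC = 0.05", "resulting in a required total sample size of 220 gymnasts (110 in each group".

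**The concern.** Group does not vary within a club. The standard error of its coefficient therefore depends mainly on the between-club variance, which is estimated from a few dozen clubs at most. Two things then go wrong in the same direction. Maximum likelihood tends to underestimate that variance when clubs are few. A normal reference also treats the variance as known. Eight reports per gymnast add observations but no clubs, so they do not cure this.

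At stake are the error rate of the one test that decides superiority in Publication I and the coverage of its headline interval. Because the reference is left open, a borderline result could also turn on a choice made after the data are seen: Wald z, likelihood ratio and t give different P-values from the same fit.

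**Working it through.** **Inputs from the SAP.** Two-sided alpha 0.05 (2.4.2); "With 80% power, 5% significance level and a decrease in the primary outcome measure from 40% to 20% in the intervention group" (2.3); mean club size 9 and ICC 0.05 (2.3); 1:1 allocation of clubs within two size strata, in blocks of 4 and 6 (2.2); eight monthly binary outcomes, group as the only fixed effect, random intercepts for club and gymnast (5.2.1).

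**Assumptions not in the SAP.** 24 clubs, 12 per arm. Gymnast share of the latent variance 0.3 or 0.5. The ICC placed on the latent scale and varied over 0.02, 0.05 and 0.10. Club sizes either all 9 or negative binomial with mean 9, variance 36 (CV 6/9 = 0.67) and a minimum of 2. All eight reports complete.

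**1. The plan's own figure.** The unpooled two-proportion formula gives (1.960 + 0.842)² × (0.4×0.6 + 0.2×0.8) / 0.2² = 7.85 × 0.40 / 0.04 = 78.5, so 79 per arm. This reproduces "at least 158 gymnasts are required". Then 158 × 1.4 = 221.2, against 220 stated, and 220 / 9 = 24.4 clubs.

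**2. Analytic check (balanced approximation).** With 24 clubs there are 22 degrees of freedom.
- Normal reference only: P(|t22| > 1.96) = 6.3%.
- Adding the maximum-likelihood variance factor: P(|t22| > 1.96 × √(22/24)) = P(|t22| > 1.88) = 7.4%.
- The second figure at other club counts: 8.8% with 16 clubs, 7.9% with 20, 7.0% with 28, 6.5% with 36.

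**3. Simulation of the stated model under no effect.** Prevalence about 40%, maximum likelihood with Gauss-Hermite quadrature, 4000 trials per row (Monte Carlo SE √(0.07 × 0.93 / 4000) = 0.4 points). Latent residual variance is 3.29. For example, at ICC 0.05 and gymnast share 0.3 the total is 3.29 / 0.65 = 5.06, giving club SD √(0.05 × 5.06) = 0.50 and gymnast SD √(0.3 × 5.06) = 1.23.

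| Club sizes | Club ICC | Gymnast share | Wald z | Likelihood ratio | t, 22 df |
|---|---|---|---|---|---|
| equal | 0.02 | 0.3 | 6.3% | 5.7% | 5.2% |
| equal | 0.05 | 0.3 | 7.4% | 6.4% | 6.0% |
| equal | 0.10 | 0.3 | 6.9% | 5.9% | 5.6% |
| equal | 0.02 | 0.5 | 5.4% | 5.1% | 4.5% |
| equal | 0.05 | 0.5 | 6.5% | 5.5% | 4.9% |
| equal | 0.10 | 0.5 | 7.2% | 6.2% | 5.7% |
| unequal | 0.02 | 0.3 | 7.1% | 6.0% | 5.6% |
| unequal | 0.05 | 0.3 | 7.7% | 6.3% | 6.1% |
| unequal | 0.10 | 0.3 | 7.2% | 6.1% | 5.8% |
| unequal | 0.02 | 0.5 | 6.6% | 5.8% | 5.1% |
| unequal | 0.05 | 0.5 | 7.9% | 6.7% | 6.2% |
| unequal | 0.10 | 0.5 | 8.1% | 6.6% | 6.3% |

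Overall, Wald z spans 5.4-8.1%, and 6.5-7.9% at ICC 0.05.

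**4. Other settings at ICC 0.05, 24 clubs** (equal sizes; then club-size CV 0.6).
- Within-gymnast correlation 0.35-0.5, 2000-3000 trials per case: Wald z 6.4-6.9%; 8.0-8.4%. With t(22): 5.2-5.4%; 6.6-6.7%.
- Gymnast share 0.4, allocation stratified and blocked as in section 2.2, 1500 trials: Wald z 6.3%; 7.8%. Likelihood ratio: 5.5%; 6.7%.
- Gymnast share 0.4, 1600 trials: Wald z about 7.6%; 8.3%. With t(22): about 6.0%; 6.5%.

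These runs are smaller, with Monte Carlo SE up to about 0.7 points, and agree with the table.

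**5. Interval.** A Wald interval excludes an odds ratio of 1 exactly when the z test rejects. Under no effect its coverage at ICC 0.05 is therefore 100 − 7.9 = 92.1% to 100 − 6.5 = 93.5%, not 95%.

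**The case against.** The SAP models clustering at both levels with a conventional method, and nothing in it is contradictory. It does not say Wald z; that is an assumption about how the stated model would be run. With a likelihood-ratio test the error is 5.1-6.7% across the table. The club count is a planning inference, and more clubs than 24 would shrink the excess. Club-size variation and within-gymnast correlation are not given. With a low ICC and equal clubs the Wald excess is only 0.4-1.3 points.

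Most of this stands, and it limits the claim to a conditional one of moderate size. It does not remove it: every Wald z scenario exceeds 5%, and at ICC 0.05 the likelihood-ratio test still shows 5.5-6.7%. Some variation in club size is to be expected, since section 2.2 stratifies at 10 gymnasts.

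Two stronger readings are tempting.
- A reader might infer that the SAP prescribes a large-sample test with a known error rate well above 5%. It does not: the reference is unstated, and the rate depends on inputs that the SAP lacks.
- A reader might extend the point to the June-only sensitivity model (5.2.3) and the UI-prevalence model (5.2.2), for which "The model will contain a random intercept for club to account for the clustering of gymnasts within clubs". Section 2.4.1 classes every analysis but the primary as supportive or exploratory. Simulation of the June-only model (4000 trials, ICC 0.05) gave 5.6% with equal clubs and 6.2% with CV 0.6 under Wald z. A t(22) reference there gave 4.3% and 4.8%, slightly conservative. The UI-prevalence model was not computed.

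**Conclusion.** The point holds for the Publication I primary model only. Section 5.2.1 fixes the estimator, the random effects and, through section 2.4.2, the alpha, but not the reference that would make the alpha true with this few clubs. Under the usual Wald z, the nominal 5% test would reject about 5.5-8% of the time under no effect, and about 6.5-8% at the SAP's ICC of 0.05, with an interval that is too narrow.

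This rests on about 24 clubs, a latent-scale ICC, complete monthly reports, and the ranges assumed for within-gymnast correlation and club size. The inflation is moderate. It deserves correction because it affects the publication's only confirmatory test and is cheap to remove.

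**What to change.** Add one of the following to section 5.2.1, for the primary outcome.

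- **Preferred.** Take the P-value from a randomisation test that re-allocates clubs following section 2.2: within the two size strata and, where feasible, within the blocks of 4 and 6. The statistic is the group coefficient of the stated model. Obtain the 95% confidence interval by inverting the same test, so that interval and P-value cannot disagree.
- **Simpler.** Take both P-value and interval from a t reference with clubs minus 2 degrees of freedom. With 24 clubs the critical value is 2.07 instead of 1.96, so for a given standard error the interval on the log-odds scale is 2.07 / 1.96 = 1.06 times as wide. State that this removes most but not all of the excess: about 5-6.7% remains, the upper end with unequal clubs.

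A randomisation P-value should not be paired with a t-based interval unless a rule says which governs when they differ.

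The cost is a few lines of SAP text, a slightly wider interval, about 1-5 points of power (simulated for the t reference) and, for the randomisation test, computing time for repeated model fits.

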3.3 Analysis Populations

The Enrolled set will include all gymnasts who have provided informed consent and have been included into the study data base.

The Full Analysis Set (FAS) will be defined as all gymnasts randomly assigned to either the intervention or control group and who have responded to:

STATISTICAL ANALYSIS PLAN for NCT05506579

- Publication I: The OSTRC-H2 questionnaire either at baseline (Oct 2022) or Nov 2022 + one or more of April, May and June 2023.
- Publication II: The ICIQ-UI-SF questionnaire at baseline and in June 2023.

The Per Protocol Analysis Set (PPS) will include all randomised gymnasts meeting the study eligibility criteria and with no major protocol deviations affecting the intervention efficacy (FAS + completed 65% or more of the intervention sessions per week).

4 Trial Population

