5.2.3 Sensitivity analyses

A sensitivity analysis of the prevalence of injuries (primary outcome in publication 1) will be performed with a mixed effect logistic regression model where only the June measurement is used as an outcome. The model will have a fixed effect for group (intervention vs control) and a random intercept for club to account for the clustering of gymnasts within clubs.

STATISTICAL ANALYSIS PLAN for NCT05506579

A sensitivity analysis of the bother of UI (primary outcome in publication 2) will be performed with a quantile (median) regression model with the June measurement as dependent variable and group (intervention vs control) and the baseline (Oct) measurement as independent variables.

6 Statistical Software

All statistical analyses will be done in Stata version 17 (StataCorp LLC, College Station, TX, USA).

7 References

Clarsen, B., et al., *The Oslo Sports Trauma Research Center questionnaire on health problems: a new approach to prospective monitoring of illness and injury in elite athletes*. British journal of sports medicine, 2014. 48(9): p. 754-760.

Clarsen, B., et al., *Improved reporting of overuse injuries and health problems in sport: an update of the Oslo Sport Trauma Research Center questionnaires*. British Journal of Sports Medicine, 2020. 54(7): p. 390-396.

Ferreira, S., et al., Reeducation of pelvic floor muscles in volleyball athletes. Revista da Associação Médica Brasileira, 2014. 60(5): p. 428-433

Olsen, O.-E., et al., Exercises to prevent lower limb injuries in youth sports: cluster randomised controlled trial. BMJ, 2005. 330(7489): p. 449.

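### The eight-month primary model for Publication I has no month term, so a seasonal trend combined with unequal monthly response by arm could bias the primary odds ratio in either direction

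*SAP*

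**What the plan says.** SAP 5.2.1 fits the monthly outcomes from November to June, without the October baseline, in one multilevel logistic model. On its terms it says: "The models will have a fixed effect for group (intervention vs control) and two random intercepts: gymnast and club", with gymnast nested in club. The result is a single number: "we will present the odds ratio (OR) for injury (with 95% confidence interval [CI]) for intervention vs control". No month, time or group-by-month term appears there or elsewhere in the SAP. Observed prevalence at each time point is shown in a figure only.

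SAP 3.3 defines the Publication I full analysis set by response to "The OSTRC-H2 questionnaire either at baseline (Oct 2022) or Nov 2022 + one or more of April, May and June 2023". A gymnast who answered at baseline and in June qualifies and contributes one of the eight outcome months.

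SAP 5.2.3 gives one sensitivity analysis of this outcome, a mixed logistic model "where only the June measurement is used as an outcome".

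**The concern.** With repeated binary outcomes and incomplete response, a likelihood-based mixed model can accommodate response that depends on arm and calendar month, but only if month is in the mean model. The gymnast and club intercepts absorb stable differences between people and clubs. They do not absorb a change over the season that everyone shares.

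Suppose prevalence rises from November to June and one arm answers less often in spring. That arm's data are then weighted towards the low-prevalence months, and its pooled odds of injury look lower whatever the programme does. Without a month term, the group coefficient is the only fixed term that can carry this difference.

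This is the single primary analysis of Publication I (SAP 2.4.1), and its two-sided test at 0.05 decides the superiority claim (SAP 2.4.2).

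**Working it through.** **1. The plan's own figure.** SAP 2.3 assumes "With 80% power, 5% significance level and a decrease in the primary outcome measure from 40% to 20% in the intervention group". With unpooled variance, n per arm = (1.960 + 0.842)² × (0.40×0.60 + 0.20×0.80) / 0.20² = 78.5, so 79 per arm and 158 in total, as stated. The design effect is 1 + (9 − 1)×0.05 = 1.4, and 158 × 1.4 = 221.2 against the stated 220. The sample size is not in dispute. The planned effect is an OR of (0.20/0.80)/(0.40/0.60) = 0.375, a log OR of −0.98.

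**2. Inputs the SAP does not give (assumptions).**
- Trend: log-odds of injury rising linearly from November to June by a total of 1.0 (control prevalence about 31% to 49%) or 2.0 (about 24% to 57%).
- Response: 95% in November, falling linearly to June. Moderate gap: 60% (intervention) vs 85% (control). Large gap: 40% vs 90%.
- Gymnast SD 1.5 on the logit scale; response independent of injury given arm and month; no club intercept simulated.

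**3. Approximation by hand.** Place the eight months at t = −0.5 to 0.5 in equal steps. The shift in log OR is roughly the total trend times the difference between arms in response-weighted mean t. The requirement of at least one April-June response divides each arm's April, May and June rates by the probability of answering at least once in those months. For the intervention arm in the large gap that probability is 1 − 0.443×0.521×0.600 = 0.861.

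- Moderate gap: mean t is −0.043 vs −0.012, a difference of −0.031. The OR ratio is exp(−0.031) = 0.97 for trend 1.0 and exp(−0.063) = 0.94 for trend 2.0.
- Large gap: mean t is −0.070 vs −0.006, a difference of −0.064. The OR ratio is exp(−0.064) = 0.94 for trend 1.0 and exp(−0.128) = 0.88 for trend 2.0.

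**4. Simulation.** 6,000 gymnasts per arm, true OR 1, April-June rule applied, random-intercept logistic model with and without month:

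| Trend | Response gap | OR without month | OR with month | Ratio |
|---|---|---|---|---|
| 1.0 | moderate | 0.957 | 0.990 | 0.967 |
| 1.0 | large | 0.938 | 1.003 | 0.936 |
| 2.0 | moderate | 0.933 | 0.993 | 0.940 |
| 2.0 | large | 0.891 | 1.009 | 0.883 |
| none | equal, moderate or large | 0.983 to 0.990 | 0.983 to 0.988 | 1.000 to 1.001 |
| 1.0 or 2.0 | equal | 0.986 to 0.992 | 0.987 to 0.992 | 0.999 |

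The simulated ratios agree with step 3. The ratio is the measure of bias, because both models share the same simulation noise.

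**5. Trial-size simulation.** 220 gymnasts, gymnast SD 2, 120 runs per setting, true OR 1:
- Trend 1.0, June response 50% vs 85%: 0.92/0.97 = 0.95.
- Trend 2.0, June response 50% vs 85%: 0.89/0.99 = 0.90.
- Trend 2.0, June response 40% vs 90%: 0.83/0.98 = 0.85.

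The step 3 approximation without the April-June rule gives exp(−0.055) = 0.95, exp(−0.109) = 0.90 and exp(−0.163) = 0.85. This suggests that the rule was not applied in these runs. In the extreme setting, applying it moves the approximate ratio from 0.85 to 0.88.

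**6. Against the trial's precision.** The shifts in step 4 are ln 0.967 = −0.03 to ln 0.883 = −0.12. A rough standard error of the log OR is 0.27 (an approximation for 110 per arm, gymnast SD 1.5, design effect 1.4). The shifts are then 0.1 to 0.4 standard errors. A nominal 5% two-sided test rejects with probability Φ(−1.96 + d) + Φ(−1.96 − d), where d is the shift in standard errors: about 5.1% at 0.03/0.27 and 7.3% at 0.12/0.27.

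**7. At the design effect.** With a true gymnast-level OR of 0.375, a trend and unequal response, the ratio was 0.957 to 1.019. With a trend and equal response it was 1.022 (0.375 vs 0.367) and 1.084 (0.401 vs 0.370): leaving month out moved the OR 2% to 8% towards 1.

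**The case against.** The strongest reply is that the harm needs two conditions and the SAP documents neither. It reports no seasonal pattern in injuries and no response by arm. Both arms receive the same questionnaire on the same monthly schedule (SAP 2.5), and one OR over the intervention period is a coherent summary of the outcome defined in SAP 5.1.1. This stands: the most that can be said is that the OR could be biased.

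A reader might infer that the omission favours the intervention because only that arm carries the burden of the programme. The SAP does not support a direction. Controls, who receive nothing, could equally lose interest, and the sign would reverse. A falling trend would reverse it too.

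The SAP also has partial safeguards. The June-only analysis cannot suffer from a mix of months, the prevalence figure would show a marked trend, and the April-June rule excludes gymnasts who stop answering early. These reduce the concern. But the June-only model drops seven of the eight months and answers a different question, so it cannot show whether the eight-month OR is distorted. The figure adjusts nothing, and the rule leaves ratios of 0.88 to 0.97 in step 4.

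Finally, a month term corrects calendar mix only. If response depends on injury status beyond what the model captures, the term does not repair that. This also stands.

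**Conclusion.** The point holds in conditional form. Pooling November to June with group as the only fixed effect leaves the primary OR open to bias if prevalence changes over the season and monthly response differs by arm. The bias can go either way. Under the stated assumptions and a true OR of 1, it is about 3% to 12% on the OR, and about 15% in the extreme setting of step 5. It is nil under the null if either condition is absent. The shift is modest against a log-OR standard error of roughly 0.3, and small beside the planned log OR of −0.98.

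The sizes rest on assumed trends, response rates and gymnast SDs. The large-sample simulation also omits the club intercept and assumes response independent of injury given arm and month. A reader might conclude that the primary result is biased or the model invalid; nothing in the SAP shows that. With similar response in the two arms, the null test is essentially unaffected. This is a near-free improvement to the primary analysis.

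**What to change.** In SAP 5.2.1, add calendar month (November to June) as a categorical fixed effect to the models for the primary and secondary injury-prevalence outcomes of Publication I. Keep the group coefficient, its confidence interval and its p-value as the primary result. Report the number and percentage of gymnasts responding by month and arm, so that readers can see whether the arms contributed different months.

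The cost is seven parameters against at most 220 × 8 = 1,760 monthly responses. With no seasonal change the OR is essentially unchanged (ratio 1.000 to 1.001). One consequence should be stated in the SAP: the reported OR becomes conditional on month as well as on gymnast and club, and with a seasonal trend it may lie slightly further from 1 than the OR without month (the 2% to 8% in step 7).

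SAP 2.5 describes data collection in the past tense, so the change should be dated and made before outcomes are examined by arm. If that moment has passed, report the month-adjusted model as a labelled sensitivity analysis.

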1.1 Background and rationale

Overuse injuries are common among competitive Norwegian rhythmic gymnasts with a mean weekly prevalence of 37% [95% CI: 36% to 39%] and incidence of 4.2 new overuse injuries [95% CI: 3.6 to 4.9] per gymnast per year (Gram, M., Clarsen, B., & Bø, K., 2021). The knees, lower back and hip/groin were the most common injury locations. It has been postulated that reduced physical capacity (e.g strength, flexibility, stability) in the knees, lower back and hip/groin can increase the risk of injuries in rhythmic gymnastics.

In addition, more than 30% of the Norwegian rhythmic gymnasts experience urinary incontinence (UI), and 70% reported that UI negatively affected sports performance (Gram, M., & Bø, K., 2020). Few of the rhythmic gymnasts had any knowledge about the pelvic floor.

Hence, this assessor blinded cluster randomized controlled trial aims to find out whether the implementation of exercises targeting reduced physical capacity and pelvic floor dysfunction can prevent/reduce the prevalence of overuse injuries and UI.

The results from this RCT will be presented in two separate publications: **Publication I** on overuse injuries and **Publication II** on UI.

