1.2.2 Secondary Objectives

Publication I: The secondary objectives are:

- I. To assess if implementation of exercises targeting reduced capacity in the lower back, knees and hip/groin reduces the prevalence of substantial overuse injuries in these areas compared with no targeted intervention.
- II. The primary objective and the secondary objective number I) including overuse injuries in the calf/ankle/foot in addition to lower back, knees and hip/groin.
- III. To assess the self-experienced effect and progress of the exercise program related to overuse injuries in the knees, lower back and hip/groin in the intervention group.

STATISTICAL ANALYSIS PLAN for NCT05506579

Publication II: The secondary objectives are:

- I. To assess if implementation of PFMT reduces the prevalence of UI compared with no targeted intervention.
- II. The primary objective and the secondary objective number I) but restricted to gymnasts having UI.
- III. The primary objective and the secondary objective number I) but restricted to gymnasts having SUI.
- IV. To assess the self-experienced effect and progress of the exercise program related to UI in the intervention group.

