5.1 Outcome Definitions

All outcomes will be analyzed on the full analysis set. An additional analysis of the primary outcome (in both publications) and the secondary outcomes I) (publication I) and I)-III) (publication II) will be performed on the per protocol set.

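### The UI self-rating of change (Publication II, secondary outcome IV) is summarised over all intervention gymnasts and should be split by UI status at baseline

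*SAP*

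**What the plan says.** Section 1.2.2 lists as secondary objective IV of Publication II: "To assess the self-experienced effect and progress of the exercise program related to UI in the intervention group". Section 2.5 specifies one 11-point global rating of change, answered once in June 2023.

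The analysis is set in section 5.2.1 for the injury rating, which is "only measured after end of the intervention (June) and only for the gymnasts in the intervention group". The summary is: "We will present the observed number and percentage of responses in each category", from -5 to 5, together with a mean and SD. Section 5.2.2 adopts this for UI in one line: "Self-experienced effect and progress will be analyzed as described in section 5.2.1".

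On the population, section 5.1 says: "All outcomes will be analyzed on the full analysis set". For Publication II, section 3.3 defines that set by response to "The ICIQ-UI-SF questionnaire at baseline and in June 2023". Having UI is not a condition of membership.

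Sections 5.1.2 and 5.1.4 repeat bother and prevalence of UI in gymnasts with UI and in gymnasts with SUI. Outcome IV has no such row. Section 1.2.3 also leaves it out of the training-load subgroups.

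**The concern.** A rating of change in a condition is easiest to read among people who had the condition. On the SAP's background figure, most intervention gymnasts may have had no UI in October. Pooling them with the affected gymnasts has two consequences.

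- The overall mean depends on how many raters had UI as well as on how those gymnasts rated their change.
- A 0 from a gymnast who never had UI looks the same as a 0 from a gymnast whose UI did not improve.

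A real perceived benefit among affected gymnasts could therefore look negligible. The SAP already restricts the bother and prevalence outcomes to affected gymnasts, so the omission here looks like an oversight. If the split is not fixed in the SAP, the choice of denominator could be made after the ratings are seen.

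**Working it through.** The SAP gives no expected value for this rating, so there is no planned figure to reproduce. The check asks how far pooling can move the reported summary.

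**Inputs**
- Prevalence of UI, p: section 1.1 says above 30% and gives no upper figure. Assumed range 30-40%, with 50% as a further case.
- Intervention-arm size: 110, the planned number per group in section 2.3 for Publication I, used for illustration. Publication II's own requirement is 21 per group; the proportions below do not depend on this choice.
- Mean rating among gymnasts with UI, a: assumed +2.
- Mean rating among gymnasts without UI, u: assumed 0, then varied.

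**Share of raters without UI**, 1 - p
- p = 0.30: 70%, or 0.70 × 110 = 77 gymnasts.
- p = 0.40: 60%, or 0.60 × 110 = 66 gymnasts.

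**Pooled mean**, p × a + (1 - p) × u

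| p | a | u | pooled mean |
|---|---|---|---|
| 0.30 | +2 | 0 | 0.30 × 2 = +0.6 |
| 0.40 | +2 | 0 | 0.40 × 2 = +0.8 |
| 0.50 | +2 | 0 | 0.50 × 2 = +1.0 |
| 0.40 | +1.5 | 0 | 0.40 × 1.5 = +0.6 |
| 0.30 | +2 | +1 | 0.60 + 0.70 × 1 = +1.3 |

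Rows one and four give the same pooled mean from different perceived benefits, because prevalence differs. In the last row, where unaffected gymnasts rate the programme mildly positively, 0.7 of the 1.3 points comes from gymnasts with no UI. The pooled mean is hard to interpret in either direction.

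**Category percentages.** Take p = 0.30, so 33 of 110 have UI. Suppose 20 of them report improvement, the other 13 answer 0, and all 77 unaffected gymnasts answer 0.
- Improved among affected: 20/33 = 61%.
- Improved as tabulated: 20/110 = 18%.
- Zeros as tabulated: 77 + 13 = 90, of which 77/90 = 86% are gymnasts without UI.

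The full distribution shows a pile-up at 0 but cannot show who is in it.

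**The case against.** The strongest reply is that the outcome is modest by design. The objective concerns perception within the intervention arm, no test or between-arm contrast is planned, and section 2.4.1 treats every non-primary efficacy analysis as supportive or exploratory. All of this is correct and keeps the severity low. It does not make the pooled UI summary readable.

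A second reply is that the item wording, and any not-applicable option, may be in the questionnaire or protocol, and that a gymnast without UI may still have something to say about the programme. This also stands: the zero for unaffected gymnasts is an assumption. However, a positive rating from them would blur the mean as well, as the last table row shows.

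A reader might infer two stronger points that the SAP does not support.

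- **That the score cannot assess effect at all.** An uncontrolled rating cannot show a causal effect, but the SAP names a self-experienced effect in one arm and bases no efficacy claim on it. Perceived change can be described.
- **That the injury rating in Publication I is biased upwards because October injuries resolve by June.** The figures in section 1.1 (37% weekly prevalence, 4.2 new overuse injuries per gymnast-year) do imply durations of only weeks. They also imply about 4.2 × 8/12 = 2.8 new injuries per gymnast over eight months, and section 2.3 assumes no change in the control group. At a stable 37%, with October and June status independent, 0.37 × 0.63 = 23% go from injured to uninjured and 23% the other way, so resolution alone gives no net shift. Splitting that rating by any injury from October to June would not help either: on the same figures and a Poisson rate, only about 0.63 × exp(-2.8) = 4% would be injury-free, and the split would condition on the post-randomisation primary outcome.

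**Conclusion.** The point holds for the UI rating in Publication II only. As planned, its summary pools gymnasts with and without UI, although the SAP separates affected gymnasts for bother and prevalence. Under the stated assumptions (30-40% with UI, +2 on average among them, 0 among the rest), the reported mean would be +0.6 to +0.8, and 60-70% of raters would have had no UI to change. The size depends on how unaffected gymnasts answer, which the SAP does not allow one to determine; that the two kinds of 0 cannot be told apart does not depend on the exact prevalence. The severity is low: this is a descriptive, last-listed secondary outcome, and neither primary analysis nor either sample size is affected.

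**What to change.** In section 5.2.2, replace the bare cross-reference with a statement that the UI rating will be presented as category counts and percentages, mean and SD, separately for intervention gymnasts with and without UI at baseline. Define baseline UI from the October ICIQ-UI-SF, using the question 6 definition that section 5.1.2 already uses for prevalence. Name the baseline-UI group as the main summary; the other row would still show ratings from gymnasts who developed UI later. Add a sentence that the rating is uncontrolled and describes perceived change only. Carry the split into the overview table in 5.1.4.

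No new data are needed, because every member of the Publication II full analysis set has a baseline ICIQ-UI-SF by definition. The cost is one table split and a few lines of text. The downside is smaller numbers in the affected row: about 33 to 44 of 110 at 30-40% prevalence (0.30 × 110 and 0.40 × 110), and fewer if the arm is smaller.
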